The authors conducted the first systematic, prospective study of resident-to-resident elder mistreatment (R-REM) in nursing homes and have developed novel methodology to identify the phenomenon. Data demonstrated that (1) R-REM is highly prevalent, (2) case finding methodology is greatly enhanced by meaningful participation of front line staff, and (3) paradoxically, higher functioning residents may be at greatest risk for involvement in R-REM (e.g., residents who are ambulatory and capable of wandering as opposed to those who are in the last stages of dementing illness). Additionally, funded by the New York State Department of Health

dementia grants program we developed a three module-program targeting front line staff to implement best practices related to R-REM in long-term services and support (LTSS) settings. Using an experimental design, we tested the intervention in nursing homes. Evaluation of longitudinal outcomes showed significant increases in staff knowledge post training, controlling for pre-training levels for the intervention group and of increased recognition of R-REM, and longitudinal reporting in the intervention as contrasted with the usual care group.¹⁸ Additionally, falls, accidents and injuries were reduced.¹⁹ These findings have important implications for assisted living residences (ALRs) where residents typically have cognitive impairment with better mobility and less staff to intervene in R-REM. The state survey process is also less uniform in ALRs (in comparison to nursing homes) and has not addressed R-REM.

Objectives

The goal of the project is to evaluate a training program for staff that enhances identification and intervention with respect to episodes of resident-to-resident elder mistreatment (R-REM). The hypotheses corresponding to the specific process outcome aims (1 & 2) and primary distal outcome (aim 3) for which the study was powered are:

Aim 1 (A1). Enhance staff knowledge of R-REM

Hypothesis 1: Staff knowledge related to R-REM and R-REM treatment will increase after training.

Aim 2 (A2). Enhance staff recognition, reporting and care planning related to R-REM

Hypothesis 2: Due to the heightened awareness as a result of training, the frequency of reported R-REM in the intervention group will increase, relative to the comparison group after training.

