There are no predetermined criteria for discontinuing or modifying the intervention.

Strategies to improve adherence to interventions

Each session is scheduled twice for all shifts, including the night staff. Additional makeup sessions are available for those staff unable to attend the original training sessions. Facility administrators alert the staff of the mandatory training sessions using several methods including flyers posted in the staff room and notices in pay stubs.

Relevant concomitant care permitted or prohibited during the trial

None

Provisions for post-trial care

There are no such provisions for this non-invasive minimal risk intervention for ALR staff.

Outcomes

Aim 1: Process level 2 evaluation of staff knowledge outcomes: Knowledge tests: Ten question pre-post knowledge tests were developed for each of the first two R-REM training modules, i.e., Recognition and Risk Factors, and Management (the SEARCH approach) based on its respective content. An additional knowledge test was developed for the third module: Implementation Guidelines, in order to assess use of the BRDS to document R-REM events. The latter test compares staff answers to the gold standard ratings. Hypothesis 1, regarding enhanced staff knowledge will be examined for individual knowledge items using paired t-tests, comparing pre-post knowledge scores between groups, adjusting standard errors for clustered data within

facilities. Group differences in total scores will be examined using a linear mixed (fixed and random effects) model for effect estimation.

Aim 2: Process level 3 evaluation of implementation outcomes: Recognition and reporting using the R-REM Measures: R-REM behavior recognition and documentation sheet (BRDS):

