Analyses for the primary hypothesis for the distal outcome: The primary analyses will examine, on an ITT basis, the differences between the usual care and intervention groups in the reduction of falls/accidents/injuries over time. Other approaches, e.g., the analysis of the “as treated” sample can result in biased estimates of the causal treatment effect due to compromised random assignment. Our primary approach to analyses is guided by our own experience,⁵⁷ and reviews.^{58,59} Depending on the level of missing data, analytic strategies (see below) can be used to address non-compliance, e.g.⁶⁰ Based on prior trials that we have coordinated, sampled from this population, 1 year attrition is between 30% and 40%; thus for 6-month data (projected attrition of 15%), the ITT analyses of all subjects will be feasible. Longitudinal analyses will include those with at least baseline and one follow-up. Sensitivity analysis will be performed using multiple imputation under different assumptions for missing data.

Because randomization is at the facility rather than individual level, imbalance may be observed on baseline variables. Preliminary analyses will be performed to determine whether the groups are balanced. Two-tailed tests of significance will be performed. Binomial tests are to be conducted on dichotomous variables, Poisson tests on nonbinomial (e.g., count) data, and *t* tests on ordinal data, adjusting standard errors for clustered data within facilities; *p* values are reported because the design does not permit randomization at the level of the individual.

Effect on likelihood of falls/injuries/accident reduction:

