Statistical models: The primary endpoint analysis for comparison between the two groups with respect to various outcomes will be based on models for the outcome at 6 and 12 months as a function of the intervention condition, adjusting for the baseline value of the outcome, i.e. an ANCOVA-type MEM analysis with intervention as a factor with two levels and baseline value as a covariate. For multiple outcomes (e.g. NIH PROMIS and FTQ) MANCOVA-type MEMs will be used to simultaneously model the multiple outcome variables. An additional factor (domain) denoting the individual outcome variables will be included in the model together with interactions between domain (depression/affect measures) and intervention. A significant interaction term would indicate that the effect of the treatment is different for affect and depression; in that case two treatment effects will be estimated for each outcome. If the interaction is not significant a model with only main effects for depression/affect and treatment will be fit and the (common) treatment effect will be estimated from this model. In addition to significance testing, we will estimate the treatment effects with 95% CI. The MEMs allow modeling the correlation between the variables assessed on the same subject and that between subjects from the same units and facilities. Group differences in total scores will be examined using a linear mixed (fixed and random effects) model for effect estimation.

The use of SAS Proc MIXED will allow for the possible group heterogeneity in residual variances that may require modeling to satisfy model assumptions and improve model fit, and the modeling of the covariance structure. In secondary analyses, we will examine within subjects change over time. We did not perform power calculations for the secondary outcomes because the most

stringent power requirements are for the primary outcome. However, we will be able to detect relatively small effect sizes, given the sample size.

Examination of the exploratory potential mediating effects of behavior on the relationship between the R-REM intervention and the falls/injuries/accident outcome will be examined using mediation analyses. Although recent evidence from Monte Carlo studies support simple joint significance tests of the mediating path coefficients,^{70,71,72} also examined will be other formal tests of mediation effects.^{73,74}

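### Hypothesis 1 is examined item by item on at least 20 knowledge questions, with no rule for which result decides it and no multiplicity control

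*Combined protocol and SAP*

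**What the plan says.** The Objectives section states Hypothesis 1 as one general, directional claim: "Staff knowledge related to R-REM and R-REM treatment will increase after training". The same section classes Aim 1 as a process aim and separates it from the primary outcome, referring to "specific process outcome aims (1 & 2) and primary distal outcome (aim 3) for which the study was powered".

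The analysis is given under Outcomes, Aim 1:

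- Material: "Ten question pre-post knowledge tests were developed for each of the first two R-REM training modules". For the last module, "An additional knowledge test was developed for the third module: Implementation Guidelines"; its number of items is not given.
- Test: "Hypothesis 1, regarding enhanced staff knowledge will be examined for individual knowledge items using paired t-tests", with standard errors adjusted for clustering within facilities.
- Total score: "Group differences in total scores will be examined using a linear mixed (fixed and random effects) model for effect estimation".

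The total-score sentence appears again in the Statistical models paragraph, which also says: "In addition to significance testing, we will estimate the treatment effects with 95% CI". No section states an alpha for Aim 1, names the score or item that decides Hypothesis 1, says how many items must be significant, or deals with multiplicity across items.

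**The concern.** The hypothesis is a single statement about knowledge, but the analysis attached to it is a set of 20 or more separate tests. When the results arrive, the trial team will hold many item p values and probably one from the total-score model, with nothing fixed in advance to say which of them answers the question. A claim that staff learned could then rest on whichever items happened to reach significance.

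The plan does set rules of this kind elsewhere. The two affect and depression measures go into a joint model, with a stated rule for when a common effect is reported. The region interaction has its own stated significance criterion. Aim 1 has no equivalent.

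It matters because knowledge is the first of the trial's stated process hypotheses. Whether staff learned anything will colour the interpretation of the falls result, whether that result is positive or null.

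**Working it through.** **The plan's own figure.** There is none to reproduce: no alpha, error rate, sample size or power is stated for Aim 1.

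**Inputs**

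- Number of items: 10 + 10 = 20 for Modules 1 and 2 (Outcomes, Aim 1). Module 3 is unstated; I assume 0 to 10 more, so 20 to 30 in all.
- Level per item: two-sided 0.05, an assumption. The plan gives alpha 0.05 only for the falls sample size. It says "Two-tailed tests of significance will be performed" in the analysis section for the primary hypothesis, not for Aim 1. The falls table does reproduce at two-sided 0.05: 403.4 and 430.3 by the Diggle formula (stated 404 and 431), and 398.0 and 424.5 by GEE (stated 399 and 425). So this is the convention used for the primary outcome.
- Direction: Hypothesis 1 needs an increase, so only a false gain counts. That has probability 0.05/2 = 0.025 per item.
- Correlation between item tests when nothing is learned: not given; I use 0 to 0.9.
- Reading rule: one significant gain would be taken as support. This is also an assumption.

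**Independent items**

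- At least one false gain among 20: 1 − 0.975^20 = 39.7%. Among 30: 1 − 0.975^30 = 53.2%.
- At least one significant item in either direction among 20: 1 − 0.95^20 = 64.2%.
- At least two false gains among 20: 1 − 0.975^20 − 20 × 0.025 × 0.975^19 = 8.8%.

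**Correlated items.** With equal correlation ρ and normal test statistics, the chance of at least one false gain among k items is 1 − ∫ φ(x) [Φ((1.96 − √ρ·x)/√(1 − ρ))]^k dx, evaluated numerically. The either-direction column uses the two-sided version.

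| ρ | 20 items, false gain | 30 items, false gain | 20 items, either direction |
|---|---|---|---|
| 0 | 39.7% | 53.2% | 64.2% |
| 0.3 | 28.0% | 35.0% | 54.0% |
| 0.5 | 21.0% | 25.5% | 41.9% |
| 0.7 | 14.5% | 16.9% | 28.9% |
| 0.9 | 7.8% | 8.6% | 15.5% |

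The comparator is one prespecified two-sided test at 0.05, with a false-gain rate of 2.5%. Even at ρ = 0.9 the rate with 20 items is about three times that (7.8/2.5 = 3.1).

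**After the change.** With total scores for three modules and a first Holm step at 0.05/3, the chance of any false result in either direction is 1 − (1 − 0.05/3)^3 = 4.9% if the modules are independent. For two modules it is 1 − 0.975^2 = 4.9%. Holm's method holds it at or below 5% under any correlation.

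**The case against.** The strongest reply has four parts.

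1. *The total score is already analysed.* A reader might infer that the plan uses the total score solely for estimation and never tests it. The text does not go that far. The mixed model examines group differences and would yield a test, and the Statistical models paragraph pairs estimation with significance testing. This part stands. The gap is narrower: the model is not named as the test of Hypothesis 1.

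2. *A false positive is not shown to be likely.* A reader might infer that a significant knowledge result is more probable than not even if nothing is learned, and cite 64%. That figure needs independent items and counts apparent declines, which cannot support a hypothesis of increase. For a false gain among 20 items the figure is 40% at most. It falls as correlation rises, and items answered by the same staff on one topic are plausibly positively correlated. It passes 50% only near 30 independent items. This part stands too.

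3. *The success rule and the 5% level are not the plan's.* Correct: the plan says that items will be examined, not that one is enough. If two significant gains were required, the independent-item figure drops to 8.8%. But the rule is absent, so nothing in the plan excludes the one-item reading.

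4. *Aim 1 is a process outcome.* Also correct, and it limits the weight of the point.

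None of this supplies a deciding analysis. The documents also give no pre-test item scores, so I make no claim about ceiling effects or about gains in power from using the total score.

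**Conclusion.** The point holds as a gap in the decision rule for a process aim. Hypothesis 1 is attached to at least 20 item-level tests, with neither a deciding result nor multiplicity control. The resulting false-gain rate for 20 items is roughly 8% to 40% over correlations of 0.9 to 0, against 2.5% for one prespecified test. Those figures rest on the assumed per-item level, the assumed correlations and the assumption that one significant gain would be reported as support. The direction of the inflation is the same in every case computed. The error rate of the primary falls analysis is untouched. This is a cheap improvement, not a threat to the trial's main conclusion.

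**What to change.** Amend the Aim 1 paragraph of the Outcomes section as follows.

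- Name the total score for each module, from the linear mixed model with clustering by facility, as the test of Hypothesis 1.
- State the contrast. The current wording combines a paired test with a comparison between groups, and the total-score model is described only in terms of group differences, whereas Hypothesis 1 is a rise after training. Usual-care facilities receive the modules only after their 12-month data collection (Intervention description), and the plan does not say whether or when their staff sit the tests for comparison. The contrast should be pre-to-post change in trained staff or, if usual-care staff take the tests at the same time, the between-group difference in change.
- State the alpha and apply Holm's method across the modules tested. Either include the Module 3 score in that family or label it descriptive.
- Report item results descriptively, as percent correct before and after with confidence intervals.

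The cost is a few sentences of SAP wording, with no new data or sample size. Item-level p values are lost. If the team wants to keep them, a Bonferroni level of 0.05/20 = 0.0025 for 20 items would hold the familywise rate at 1 − 0.9975^20 = 4.9%, but that answers a question about single items, not the hypothesis as stated.

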- 1) If the resident has a perceptual impairment that makes it difficult for her/him to read/sign the Informed Consent Form (e.g., visual impairment)
- 2) If the resident is illiterate, the interviewer reads the Informed Consent Form to the resident

3) If the resident has a physical impairment that prevents her/him from writing (e.g., contractures in both arms, paralysis, etc.)

4) If the resident does not wish to sign the Informed Consent Form, but verbally indicates that s/he is willing to participate in the interview

Per the IRB, in these cases, an observer not associated with the research (e.g., facility staff) must witness the verbal consent process.

Interventions

Explanation for the choice of comparators

After successful implementation of the R-REM research protocol in nursing homes, the authors wanted to further test the intervention in another LTSS setting with a similar population but with less staffing and state oversight. Assisted living was selected because it is an area of LTSS that is growing rapidly both in numbers of facilities and in terms of the populations served.

Intervention description

The intervention, i.e., the training of nursing, social work, administrative and other staff on R-REM is conducted in three separate sessions: 1) Recognition and Risk Factors, 2) Management, and 3) Implementation of Guidelines. The trainer who administers the three modules is an experienced doctoral level, adult education professional who participated in the development and modification of the modules; she has extensive experience in staff training. Modules are provided to facilities randomized to the intervention after the completion of baseline data collection, and to those randomized to usual care after completion of 12-month follow up data collection.

Description of Module 1: Recognizing R-REM: Module 1 covers the extent of R-REM which includes: evidence; risk factors associated with the victims, perpetrators, and environment; and the role of cognitive impairment. Different forms of mistreatment are covered, including physical, psychological, sexual, and theft. This module is delivered in the form of an experiential half-hour in-service training, plus pre- and post-tests designed to be conducted at the ALRs.

Description of Module 2: Management of R-REM

- A. Introduction and review of previous session and pretest
- B. Film on management of elder mistreatment

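### Aim 1 plans a between-group comparison of knowledge gains, but the only tests described for Modules 1 and 2 sit inside training that both arms receive, so that comparison cannot show whether training works

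*Combined protocol and SAP*

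**What the plan says.** Under Objectives, Hypothesis 1 reads: "Staff knowledge related to R-REM and R-REM treatment will increase after training". No comparison arm is mentioned. Hypothesis 2, the primary hypothesis and both secondary hypotheses do name the comparison group.

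Under Outcomes, Aim 1, individual knowledge items are to be analysed with paired t-tests, "comparing pre-post knowledge scores between groups", with standard errors adjusted for clustering by facility. For totals, "Group differences in total scores will be examined using a linear mixed (fixed and random effects) model for effect estimation".

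Under Intervention description, the tests belong to the sessions. Module 1 is a half-hour in-service, "plus pre- and post-tests designed to be conducted at the ALRs". The Module 2 outline lists a pretest in its first item and a post-test in its last. Intervention facilities get the modules after baseline data collection. Usual-care facilities get the same modules later: they go "to those randomized to usual care after completion of 12-month follow up data collection".

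Under Plans for assessment and collection of outcomes, the Aim 1 data are these module tests, listed apart from the five sources for Aims 2 and 3. Neither testing dates nor arms are given.

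**The concern.** The hypothesis is about change within staff, while the analysis is worded as a contrast between arms. A between-arm contrast of gains measures the effect of training only if one arm is untrained between its two tests. For Modules 1 and 2 the documents describe no such arm: a pre/post pair from usual-care staff, taken where the modules place it, also spans training.

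The item-level wording also conflicts with itself. A paired t-test compares two scores from the same person; it does not compare one arm with the other.

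If the between-group result is taken as the test of Hypothesis 1, an effective programme could produce a null result and be reported as having failed to raise knowledge. Equally, a difference caused by when the arms were trained could be reported as evidence that training works.

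**Working it through.** The plan gives no sample size, expected gain or variance for Aim 1. Its power calculation covers falls only, so there is no plan figure to reproduce here.

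**Inputs from the documents**
- Modules 1 and 2 each have a ten-question pre/post test (Outcomes, Aim 1).
- Those tests sit inside the sessions (Intervention description).
- Sessions come after baseline in the intervention arm and after month 12 in usual care (Intervention description).
- There are 6 facilities per arm (Sample size), and tests are two-sided (Statistical methods).

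**Assumed inputs, for illustration only**
- True gain g of 0.5 to 2 points out of 10, SD of individual gains 1.8, facility ICC 0.05, and 40 staff tested per facility.

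**Estimand.** The between-group contrast of gains is D = E(gain, intervention) − E(gain, usual care).

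*Case A: usual-care pairs come from their own later training.* With equal gains, D = g − g = 0 for every g.

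Now let a year of exposure raise the usual-care pre-test by h and leave the post-test unchanged. The usual-care gain is then g − h, and D = g − (g − h) = h. The training gain g cancels, so D measures the head start.

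*Case B: untrained usual-care staff sit both tests on the intervention calendar.* With a retest effect r common to both arms, D = (g + r) − r = g. This contrast does measure training.

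*Case C: within-staff change in the intervention arm alone.* The expectation is g + r. It responds to training but does not separate it from retesting.

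**Simulation check.** This used 4,000 replicates and a t-test on facility mean gains. Under the assumed inputs the variance of a facility mean gain is 1.8² × (0.05 + 0.95/40) = 3.24 × 0.07375 = 0.239. The standard error of D is √(2 × 0.239/6) = 0.28.

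| True gain g | Case A: mean D | Case A: rejection | Case B: mean D | Case B: rejection |
|---|---|---|---|---|
| 0.5 | 0.000 | 5.1% | 0.50 | 36.6% |
| 1.0 | −0.005 | 5.2% | 1.00 | 89.2% |
| 1.5 | −0.001 | 5.1% | 1.50 | 99.8% |
| 2.0 | −0.001 | 4.7% | 2.00 | 100% |

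The Case B percentages depend on the assumed SD, ICC and staff numbers. The zero in Case A does not; it depends only on equal gains.

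**Which case does the plan describe?** The testing in Intervention description leads to Case A. Case B needs tests of untrained usual-care staff, which no section schedules. By contrast, the section on observational data does say when usual-care staff receive their behavior recognition and documentation sheet (BRDS) pads.

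**Module 3.** Its test is scored against gold-standard ratings and no pre-test is described. There is no pre/post gain to difference, so the algebra above does not apply directly.

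**The case against.** A reader might infer that the design guarantees a null result. The documents do not support that. They never say that the tests after month 12 supply the usual-care data for Aim 1, and they do not rule out earlier testing. If untrained usual-care staff were tested concurrently, the expected difference would be the full training gain. This objection stands, and it makes the zero conditional on the testing described.

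A reader might also infer that Hypothesis 1 cannot be tested at all. That goes too far. The plan names paired t-tests on pre/post scores, and such a test, read plainly, addresses a gain within staff. The Background's account of the nursing-home trial, a knowledge gain after training in the intervention group adjusted for pre-training level, fits that reading. The fault is confined to the between-group wording and the group-difference model.

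The mixed model is specified for total scores, not explicitly for gains. Trained intervention scores set against usual-care scores taken before training would not have zero expectation. That is true, but the plan does not say which scores enter. If they came from the tests described, the usual-care pre-training scores would date from after month 12, so arm and calendar time would be mixed.

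Equal gains are not assured. Usual-care staff receive BRDS pads when their unit opens, and staff informants are interviewed about R-REM at three waves. Either could shift later pre-test scores. This weakens the exact zero but does not rescue the contrast, because the resulting difference is the head start h.

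Finally, dropping the group comparison gives up a randomised contrast for an uncontrolled one. That is a real cost, but a randomised contrast of trained with untrained staff exists only if untrained staff are tested.

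**Conclusion.** The point holds in conditional form, for Modules 1 and 2. The stated analysis does not match its hypothesis. On the only testing described, a between-group contrast of gains has expectation zero for any training effect when gains are equal, with rejection at about the nominal 5%. When gains are unequal, the contrast reflects timing or prior exposure and not whether training works.

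This rests on two assumptions: that usual-care scores come from the tests built into their own later sessions, and, for the exact zero, that training works equally in both arms. The first is an inference from an unspecified schedule. The knowledge gains, SD, ICC and staff numbers used for illustration do not affect the zero.

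The consequence is limited to a process aim. The falls analysis and its sample size are untouched. It should still be corrected, because Aim 1 is a named hypothesis and the correction is cheap.

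**What to change.** For Modules 1 and 2:

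- Define the test of Hypothesis 1 as the within-staff post-minus-pre change in the intervention facilities, allowing for clustering by facility. One suitable form is a mixed model for the pre and post scores with random effects for staff and facility.
- Report the usual-care facilities' later gain as a replication.
- Remove the between-group gain comparison as the test of Hypothesis 1, and state what the total-score mixed model compares.
- Describe the result as an uncontrolled pre/post change that is open to retest effects.

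Keep a between-group test only if the plan states that untrained usual-care staff are tested on the same calendar as the intervention arm and that those scores are the comparator.

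For Module 3, state separately what is compared, since no pre-test is described.

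Cost: analysis-plan wording only, with no new data. The price is the loss of a control group for this aim. Keeping the between-group option would require concurrent usual-care testing, which is extra data collection if it is not already being done.
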